## 1. STUDY DESIGN

### 1.1. STUDY OBJECTIVES

#### 1.1.1. Primary Objective

The primary objective of the study is to evaluate the efficacy in terms of the percentage of subjects achieving an ACR20 response, of different doses and dose regimens of GLPG0634 compared to placebo at Week 12.

#### 1.1.2. Secondary Objectives

The secondary objectives of the study are:

- To evaluate the efficacy in terms of the percentage of subjects achieving an ACR20, ACR50, ACR70, ACR-N, DAS28(CRP), EULAR response and ACR/EULAR remission, CDAI, and SDAI with different doses and dose regimens of GLPG0634 compared to placebo at every visit.
- To evaluate the safety and tolerability of different doses and dose regimens of GLPG0634 in comparison with placebo.
- To characterize the population PK and PD of GLPG0634 and its metabolite (G254445) in subjects with rheumatoid arthritis and investigate the relationship between exposure and efficacy/safety/PD.
- To evaluate the effects of different doses and dose regimens of GLPG0634 administration on subjects' disability, fatigue, and quality of life.

## 1.2. STUDY DESIGN

This is a multicenter, phase IIb, double-blind, placebo-controlled add on study in subjects with moderately to severely active RA who have an inadequate response to MTX. A total of 595 subjects will be randomized to one of 6 dose regimens of GLPG0634 or to placebo, on top of their stable dose of MTX. Treatment duration will be 24 weeks. At Week 12, subjects on placebo who have not achieved a 20% improvement in swollen joint count (SJC66) and tender joint count (TJC68) will be re-randomized (automatically via interactive voice/web response [IXRS]) to treatment to receive GLPG0634 100 mg q.d. or 50 mg b.i.d. doses in a blinded fashion, subjects on 50 mg q.d. who have not achieved a 20% improvement in SJC66 and TJC68 will be assigned to 100 mg q.d. and subjects on 25 mg b.i.d. who have not achieved a 20% improvement in SJC66 and TJC68 will be assigned to 50 mg b.i.d. All will continue the study until Week 24. Subjects in the other treatment groups will maintain their randomized treatment until Week 24.

Upon qualification for the study, subjects will be randomized to placebo or one of 6 dosing regimens in a 1:1:1:1:1:1 ratio (N=85 for each treatment group; total N=595), stratified by geographic region and previous use of a biological DMARD during a single clinical study setting.

[figure not shown]
Subjects participating in the study will be requested to attend a maximum of 11 visits throughout the study: Screening visit (up to 28 days before Baseline visit), Baseline visit, Week 1 visit, Week 2 visit, Week 4 visit, Week 8 visit, Week 12 visit, Week 16 visit, Week 20 visit, Week 24 visit (and potentially a follow-up visit). At completion of the 24-week

treatment period, subjects will be offered the option to enter a Long Term Follow-up study (GLPG0634-CL-205). For the subjects not entering the GLPG0634-CL-205, an additional final Follow-up visit will be scheduled 7 to 10 days after end of study treatment.

Consequently, each subject will remain in the study for a maximum of 29 weeks (from Screening visit to Follow-up visit).

Data from the Long Term Follow-up study 205 will be presented in a separate analysis, and is not part of this SAP.

#### GLPG0634-CL-203 (DARWIN 1): add-on treatment to methotrexate:

#### Notes:

- R = (re)randomization.
- Responder: at least 20% drop in TJC68 and SJC66 versus baseline.

### 1.3. PROTOCOL AND PROTOCOL AMENDMENTS

Protocol Versions	Date (ddMMMyyyy)
Final 1	14MAR2013
Amendment 1	11APR2013
Amendment 2	17APR2013
Amendment 3	02AUG2013
Amendment 4	20NOV2013
Amendment 5	20MAY2014

This SAP was based on the latest version of the protocol (Amendment 5, 20MAY2014).

### 1.4. FLOWCHART

Event	Screening	Baseline 	Treatment period 									FU visit 
			D8/ W1	D15/ W2	D29/ W4	D57/ W8	D85/ W12	D113/ W16	D141/ W20	D169/ W24	EDV 	
Informed consent	Written informed consent will be obtained before any study-related procedures and/or assessments are performed.											
Inclusion/ exclusion criteria	X	X 										
Demographic data and baseline disease characteristics	X											
Medical history/ concomitant illnesses	X											
Physical examination	X 	X					X			X	X	X
Serology 	X											
TB test and chest X-ray 	X											
Pregnancy test 	X	X	X	X	X	X	X	X	X	X	X	X
12-Lead ECG	X						X			X	X	X
Vital signs 	X	X	X	X	X	X	X	X	X	X	X	X
Clinical laboratory tests 	X	X	X	X	X	X	X	X	X	X	X	X
PK blood samples 					X		X			X	X	
PD blood samples 		X	X		X		X			X	X	

 Subjects will begin to take their treatment on the next morning (Day 1) following randomization.

 During the treatment period, a visit time window of ± 2 calendar days is allowed.

 Follow-up visit will be performed only for subjects discontinuing prematurely from the study and for subjects not entering the Long Term Follow-up study GLPG0634-CL-205.

 Early discontinuation visit.

 Eligibility criteria check based on the laboratory results from the Screening visit.

 At Screening, includes height and weight.

 Includes Hepatitis B and C, HIV 1 and 2, RF, and anti-CCP.

 X-ray should be performed if results from an X-ray performed in the previous 3 months are not available at the site.

 For female subjects only. To be performed on serum at Screening and Week 24/EDV and on urine for other visits.

 Vital signs are defined as blood pressure (systolic and diastolic), HR, and oral temperature.

 Refer to protocol Section 9.7.1.4.2..

 PK samples: 1 blood sample (2 mL) for analysis of GLPG0634 and its main metabolite (G254445) in plasma.

 PD samples: 4 blood samples (2x4 mL for serum preparation and 2x2.5 mL in PAXgene tubes) will be collected for analysis of serum (analytes and miRNA profiling) and whole blood (gene expression in circulating leukocytes, mRNA and miRNA profiling).

Event	Screening	Baseline 	Treatment period 									FU visit 
			D8/ W1	D15/ W2	D29/ W4	D57/ W8	D85/ W12	D113/ W16	D141/ W20	D169/ W24	EDV 	
Randomization		X 					X 					
IXRS call	X	X	X	X	X	X	X	X	X	X	X	
Dispense study medication		X	X	X	X	X	X	X	X			
Subject diary card dispensation 		X	X	X	X	X	X	X	X			
Subject diary card collection			X	X	X	X	X	X	X	X	X	
Drug accountability check			X	X	X	X	X	X	X	X	X	
Study medication dosing												
Serum CRP	X	X	X	X	X	X	X	X	X	X	X	
SJC66	X	X	X	X	X	X	X	X	X	X	X	
TJC68	X	X	X	X	X	X	X	X	X	X	X	
Physician's Global Assessment		X	X	X	X	X	X	X	X	X	X	
Patient's Global Assessment	X	X	X	X	X	X	X	X	X	X	X	
HAQ-DI		X	X	X	X	X	X	X	X	X	X	
FACIT fatigue scale		X			X		X			X	X	
SF-36 questionnaire		X			X		X			X	X	
AE assessment												
Concomitant medications												

 Subjects will begin to take their treatment on the next morning (Day 1) following randomization.

 During the treatment period, a visit time window of ± 2 calendar days is allowed.

 Follow-up visit will be performed only for subjects discontinuing prematurely from the study and for subjects not entering the Long Term Follow-up study GLPG0634-CL-205.

 Early discontinuation visit.

 Upon qualification for the study.

 At Week 12, subjects on placebo who have not achieved a 20% improvement in SJC66 and TJC68 will be re randomized (automatically via IXRS) to treatment to receive GLPG0634 100 mg q.d. or 50 mg b.i.d. doses in a blinded fashion, subjects on 50 mg q.d. who have not achieved a 20% improvement in SJC66 and TJC68 will be assigned to 100 mg q.d. and subjects on 25 mg b.i.d. who have not achieved a 20% improvement in SJC66 and TJC68 will be assigned to 50 mg b.i.d. All will continue in the study until Week 24. Subjects in the other groups will maintain their randomized treatment until Week 24.

 Subject diary card will be dispensed to subjects on D -1 and at every following visit; subjects should be instructed to bring their diary card along with them to all visits.

## 2. ANALYSIS POPULATIONS AND TREATMENT GROUPS

### 2.1. ANALYSIS CHAPTERS

Each part of the analysis will consist of 2 or 3 main chapters:

1. Chapter 1: Period 1 of the study (up to and including Week 12): safety
2. Chapter 2: The study as a whole (periods 1 and 2 together, spanning the entire 24 weeks): safety and efficacy
3. Chapter 3: Period 2 of the study (from Week 12 until the end of the study): only for efficacy and adverse events.

Each analysis chapter will use its own set of “treatment groups” and imputation methods. Later in this document, when all parameters are analyzed separately, will be mentioned which is the primary.

#### 2.1.1. Efficacy data

Study period	Treatment groups	Analysis populations	Imputation method
“Chapter 2”: Periods 1+2 together (full 24 weeks period)	
The 7 original groups:
 
 
– Placebo
 
– GLPG0634 q.d. dosing groups:                             
 
• 50 mg q.d.
 
• 100 mg q.d.
 
• 200 mg q.d.
 
 
 
– GLPG0634 b.i.d. dosing groups:                             
 
• 25 mg b.i.d.
 
• 50 mg b.i.d.
 
• 100 mg b.i.d.
 
 
 
 
For the subjects in the placebo and low dose groups who switched to 100 mg/day during the second study period: they will be handled as if they discontinued at Week 12, and will be imputed from Week 12 onwards in the second study period.                      (Details: see further in the SAP)
	
ITT: all subjects randomized, exposed at least once, and with post-baseline data for at least one efficacy parameter.
 
Per-protocol: subpopulation of ITT, excluding all critical (=major) protocol deviations. This is decided during the blind review meeting before final database lock.
	
Observed case, non-responder imputation (NRI), last observation carried forward (LOCF): depending on the parameter; is specified later when all parameters are discussed.

Study period	Treatment groups	Analysis populations	Imputation method

“Chapter 3”: Period 2, as of Week 12
	
The Week 12 responders, remaining on the same treatment during the second study period: 7 treatment arms:
 
 
– Continued placebo
 
– Continued GLPG0634 50 mg q.d.
 
– Continued GLPG0634 100 mg q.d.
 
– Continued GLPG0634 200 mg q.d.
 
– Continued GLPG0634 25 mg b.i.d.
 
– Continued GLPG0634 50 mg b.i.d.
 
– Continued GLPG0634 100 mg b.i.d.
 
 
This analysis will show whether Week 12 responders remain responders when treatment is continued unchanged.
 
The Week 12 non-responders, either “switching” to 100 mg/day or continuing the same mid/high dose during the second study period:
 
 
– Placebo non-responders switched to GLPG0634 100 mg q.d.
 
– GLPG0634 50 mg q.d. non-responders switched to GLPG0634 100 mg q.d.
 
– Continued GLPG0634 100 mg q.d.
 
– Continued GLPG0634 200 mg q.d.
 
– Placebo non-responders switched to GLPG0634 50 mg b.i.d.
 
– GLPG0634 25 mg b.i.d. non-responders switched to GLPG0634 50 mg b.i.d.
 
– Continued GLPG0634 50 mg b.i.d.
 
– Continued GLPG0634 100 mg b.i.d.
 
 
This analysis will show whether Week 12 non-responders start to respond when either treated for a longer period with the same mid/high dose, or have a dose increase to 100 mg/day.
	
ITT: all subjects randomized, exposed at least once, and with post-Week 12 data for at least one efficacy parameter. Subjects who discontinued prior the Week 12 visit will be excluded from this analysis.
	
Observed case, non-responder imputation (NRI), last observation carried forward (LOCF): depending on the parameter; is specified later when all parameters are discussed.

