#### **8.8.1.1 Datasets or Populations Analyzed**

All randomized subjects who received at least one dose of study medication and have at least one post-Baseline efficacy assessment will be included in the efficacy analysis (intent-to-treat [ITT]).

A secondary per-protocol analysis will be performed to confirm the ITT analysis, excluding subjects with major protocol deviations (such as Baseline CRP within normal range, Baseline TJC68 <8, Baseline SJC66 <6, <80% study medication compliance, or use of forbidden concomitant medications). Full details of the major protocol deviations will be described in the statistical analysis plan, with adherence to analysis sets agreed upon prior to database lock and unblinding.

All randomized subjects who received at least one dose of study medication will be included in the safety analysis.

All randomized subjects who received at least one dose of GLPG0634 and who have at least one PK measurement will be included in the PK analysis.

Reasons for study termination will be tabulated.

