## 6.2. INTERIM ANALYSIS

Note that a DSMB is installed to monitor unblinded safety data during the course of the study. This is described in a separate DSMB Charter and DSMB SAP.

An unblinded interim analysis will be performed when all subjects have reached Week 12 (or have discontinued before Week 12). Only data from this study period will be included in the interim analysis.

The analysis will not present everything, but only a selection of parameters:

- General: region and county distribution, trial termination reasons, demographics and baseline disease characteristics.
- Efficacy: ACR20/50/70, ACR-N, SDAI and CDAI, DAS28(CRP), the ACR components (joint counts, CRP, HAQ-DI and the 3 VAS scores).
- Safety: adverse events, laboratory safety and vital signs.

The exact tables and figures to be produced for this interim analysis are identified in the next sections where all the TLFs are defined. The interim analysis is intended to support preliminary dose selection for the GLPG0634 phase III program.

Because this efficacy analysis consists of parts of the full Week 12 primary analysis, there is no inflation of the type-I error rate, and therefore no statistical correction is applied.

To preserve the blind for Team members who have access to raw patient data, the following approach will be used:

The statistical analysis of the unblinded data will be handled by a statistician at [REDACTED] who is independent from the regular study team. The regular study team (including [REDACTED] lead statistician and corresponding [REDACTED] biometrics team) will remain blinded.

This interim analysis output will comprise summary tables and plots, but no listings. These summary results will be viewed by the sponsor, but no individual subject data (such as listings or datasets) will be exchanged.

To prevent accidental unblinding of specific subjects, the following rules will also be applied:

- For descriptive statistics: min-max lines will be suppressed.
- For frequency tables containing small numbers of subjects in some categories (e.g., trial termination reasons, demographics/baseline characteristics, AEs & SAEs, and lab & vital signs abnormalities), the following rules will be programmed in the tables:
  - If there are events in multiple groups, including the placebo group: the full details will be shown in the table, per treatment group. This does not cause any unblinding of specific subjects.

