## 7.2. PROTOCOL DEVIATIONS AND ELIGIBILITY

Protocol deviations are determined and recorded whilst the study is ongoing, and the list is finalized prior to final database lock (and unblinding). All deviations are classified as either “critical” or “non-critical”. Only the critical (=major) protocol deviations will be presented in the tables. For more details, please refer to the Protocol Deviation Plan.

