**Table 14.2.1.1.10: ACR20 at Week 12: Tabulation versus baseline characteristics**

The table will show two methods of imputing missing values: LOCF and NRI.

Frequency tabulation of the ACR20 response rate at Week 12 per treatment group, split up according to the following baseline categories:

- Demographics:
  - Region (as used in the central randomization)
  - Country
  - Gender
  - Age categories:
    - < 45 ;
    - [45,65[ ;
    - [65,75[ ;
    - ≥ 75 years
  - BMI categories:
    - ≤ 18.5;
    - ] 18.5 , 25.0 ] ;
    - ] 25 , 30 [,
    - ≥ 30 kg/m^2
- Baseline disease characteristics:
  - Duration of RA:
    - < 1;
    - [ 1 , 2 [ ;
    - [ 2 , 5 [ ;
    - [ 5 , 10 [ ;
    - [ 10 , 20 [ ;
    - ≥ 20 years
  - Baseline CRP:
    - <0.7 x ULN;
    - [0.7,1.0] x ULN;
    - ]1.0,1.2[ x ULN;
    - ≥ 1.2 x ULN
  - Baseline TJC68: < 20, ≥ 20
  - Baseline SJC66: < 20, ≥ 20
  - Baseline DAS28(CRP): high, moderate, low, remission (see further section on DAS28 for the definition of these categories)
  - RF status
  - Anti-CCP status
  - Previous use of:
    - Biological (anti-TNF or other biological DMARD) yes/no,
    - anti-TNF yes/no,
    - other biological DMARD yes/no,
    - conventional DMARD yes/no,
    - NSAID yes/no,
    - steroid yes/no,

- analgesic yes/no,
- other RA medication yes/no.

Population: ITT.

Table to be created for the Week 12 interim analysis as well.

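### The Week 12 per-protocol set is fixed only before final lock, after the sponsor has viewed unblinded Week 12 ACR20 by arm and by Baseline CRP class

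*SAP*

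**What the plan says.** Protocol 8.8.1.1 makes the per-protocol analysis a secondary one whose purpose is to confirm the ITT result. It describes the set by examples only: "excluding subjects with major protocol deviations (such as Baseline CRP within normal range, Baseline TJC68 <8, Baseline SJC66 <6, <80% study medication compliance", and so on. It makes two commitments: "Full details of the major protocol deviations will be described in the statistical analysis plan", and this is to be done "with adherence to analysis sets agreed upon prior to database lock and unblinding".

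The SAP defines per-protocol as ITT without critical (that is, major) deviations. On timing, SAP 2.1.1 says: "This is decided during the blind review meeting before final database lock". SAP 7.2 says that deviations are recorded as the study runs and that "the list is finalized prior to final database lock (and unblinding". It does not list the critical deviations. Instead it says: "For more details, please refer to the Protocol Deviation Plan".

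SAP 6.2 schedules an unblinded interim once every subject has reached Week 12 or has dropped out. On access it says: "These summary results will be viewed by the sponsor, but no individual subject data (such as listings or datasets) will be exchanged". The interim package includes Table 14.2.1.1.10, Week 12 ACR20 by arm within Baseline classes: "Table to be created for the Week 12 interim analysis as well". Table 14.2.1.4.7 does the same for the change in DAS28(CRP).

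**The concern.** A per-protocol analysis supports the ITT result only if its membership was settled without knowledge of the outcome. In this trial the Week 12 outcome is known, by arm, well before final lock. Once the sponsor has seen how a class of subjects responded in each arm, a decision on whether that class counts as a critical deviation is no longer blind to its consequence. Withholding individual treatment codes does not prevent this, because the decision applies to a class rather than to named subjects. At stake is how far the Week 12 per-protocol tables can confirm the primary analysis: ACR20 under NRI and LOCF, DAS28(CRP) and EULAR response, each with six comparisons against placebo.

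**Working it through.** No figure in the plan is disputed. The check concerns the order of events and whether the interim tables match the deviation classes.

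**Order of events**

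1. There are two locks, interim and final (Protocol 8.8.1; SAP 6.3.1 and 6.3.2).
2. The interim follows the first lock. It is unblinded, and the sponsor views its summary tables (SAP 6.2). Protocol 8.8.1.5 says that it matches the full Week 12 primary analysis.
3. Per-protocol membership and the deviation list close before the second lock (SAP 2.1.1 and 7.2). Nothing ties either to the first.
4. The interim ACR20 tables are ITT only. The per-protocol versions of the same Week 12 comparisons come at the final analysis (Tables 14.2.1.1.1 to 14.2.1.1.3).

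So Week 12 per-protocol membership closes after the Week 12 by-arm result has been seen.

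**Do the interim splits match deviation classes?**

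| Split in Table 14.2.1.1.10 | Corresponding limit | Match |
|---|---|---|
| Baseline CRP at 1.0 x ULN | Normal Baseline CRP, example in Protocol 8.8.1.1 | Yes |
| Baseline CRP at 0.7 x ULN | Screening CRP at 0.7 x ULN, Protocol 8.3.2 criterion 3 | No, different visit |
| TJC68 at 20 | 8 | No |
| SJC66 at 20 | 6 | No |
| Country | None | No |
| Prior therapy, yes/no | Permitted versus prohibited use, Protocol 8.3.3 | No, the split does not separate them |

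The tables of deviations (14.1.2.1), compliance (14.1.4.1) and concomitant therapy (14.1.3.18) are not marked for the interim.

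**The CRP case**

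SAP 8.8.1 gives the ULN as 8.999 in a section reported in mg/L, and treats values up to the ULN as normal. The Screening threshold is therefore 0.7 x 8.999 = 6.30 mg/L. A subject with CRP between 6.30 and 8.999 mg/L at Screening is eligible. If Baseline is similar, the same subject falls within the protocol's example of a major deviation. Whether such a subject is critical has to be decided, and SAP 2.1.1 and 7.2 do not decide it. In Table 14.2.1.1.10 the classes below 0.7 and from 0.7 to 1.0 x ULN together make up the normal range, so their by-arm ACR20 is visible at the interim.

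**Size**

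The documents give no number of subjects in any deviation class, so the following is assumption only. Take placebo at 25/85 (29.4%) and one active arm at 41/85 (48.2%), a difference of 18.8 points. Suppose that a reclassified type holds four responders in an arm:

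- Placebo only: 21/81 = 25.9%; difference 48.2 - 25.9 = 22.3, a shift of +3.5 points.
- Both arms: 37/81 = 45.7% against 25.9%; difference 19.8, a shift of +0.9 points (unrounded 18.82 to 19.75).
- Active arm only: 45.7 - 29.4 = 16.3, a shift of -2.6 points (unrounded 18.82 to 16.27).

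Even the sign depends on the assumption.

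**The case against.** The strongest reply is that the decision belongs to a blind review meeting and that the blind is protected. An independent statistician runs the interim, the lead statistician and regular study team stay blinded, no listings or datasets leave, and sparse cells that would identify treatment are blanked (SAP 6.2). SAP 5.2 lists a procedure for blind review. No passage says that sponsor staff who saw the interim take part in the classification. The Protocol Deviation Plan may have set the criteria long before. The one CRP cut that does match was named in the protocol in advance. The protocol does not say which lock it means, and the unblinding in SAP 7.2 can be read as release of codes to the study team. Finally, the per-protocol analysis is secondary in a phase IIb study, and no decision rule rests on it.

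Most of this stands, and it limits the point. Two parts do not remove it. First, no passage bars those who saw interim results from the blind review, and some interim knowledge did reach the plan: the change list for SAP version 5.0 (SAP 6.3.2) justifies a change to the VAS plots by what the interim showed. That change is harmless, but it shows that the separation was not complete. Second, naming normal Baseline CRP as an example does not settle it, because the eligibility rule admits subjects who can meet it and the promised full list is not in SAP 2.1.1 or 7.2.

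**Conclusion.** The point holds on timing. For the Week 12 endpoint, per-protocol membership and the deviation list close after the sponsor has seen unblinded by-arm results, which does not meet the commitment in Protocol 8.8.1.1. Normal Baseline CRP is the one class shown to be both open to decision and visible by arm at the interim.

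A reader might infer more, and the documents do not support it:

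- That the interim shows results for joint-count, country or prior-therapy deviations. Those splits do not match deviation classes.
- That the classification rules themselves were written after the interim. The Deviation Plan is not available, and its date is unknown.
- That the set was changed in the light of the results. The version 5.0 change list records no change to the per-protocol definition or its timing.
- That the SAP's reference to unblinding is false. On the narrower reading, release of individual codes, it is true, but it then gives no protection against knowledge of by-arm results.
- That every difference would move by about 3.5 points. That needs exclusions on placebo only, and responders only.

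The effect on the secondary per-protocol results cannot be sized from the documents. The primary analysis, ACR20 at Week 12 in ITT with NRI, is unaffected.

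**What to change.** In SAP 2.1.1 and 7.2, hold the blind review of deviations up to Week 12 before the interim lock. Classify them there, including whether an eligible subject with a normal Baseline CRP is critical. Freeze the Week 12 per-protocol list and use it for every Week 12 per-protocol table. At final lock, classify only deviations that arise later, for the Week 16 to 24 tables.

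SAP version 5.0 post-dates the interim lock, so the fallback may be what applies. If the interim has been delivered, use the Protocol Deviation Plan criteria as dated before the interim lock, restrict the blind review to people with no access to interim output, record who attended, and label any later reclassification post hoc.

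The cost is one review held earlier and some SAP wording. The drawback is that period-1 deviations found late cannot enter the frozen list and go into a labelled supplementary analysis. Deviations are already recorded while the study runs, so most of the material for an earlier review should exist.

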### ***6.6 Rationale for the Study***

Over the last decade changes in RA treatment strategies, accompanied by advances in drug development and the addition of targeted biological therapies, have greatly improved the outcomes for patients with RA. Despite these developments, therapeutic challenges have remained, since current conventional and biological DMARDs sometimes fail or produce only partial response. Therefore there is still a need for orally administered novel therapies with a

different mechanism of action that can effectively modify the disease course and that are safe and well tolerated.

GLPG0634 is a small molecule for oral daily administration that has shown promising results as a potentially safe and effective RA treatment. Study GLPG0634-CL-203 is a therapeutic phase IIb dose-finding study to compare 3 daily doses (50 mg, 100 mg and 200 mg) of GLPG0634 and 2 dose regimens (q.d. and b.i.d.) versus placebo to be administered daily for 24 weeks in subjects with established RA, who have moderately to severely active disease despite MTX treatment. The aims of the current study are to evaluate the efficacy of varying doses and regimens of GLPG0634, to identify the minimally and optimally effective dose, and to assess the safety and tolerability, as well as to describe the PK and PD parameters of the compound in this subject population.

MTX is the most commonly prescribed conventional DMARD in RA treatment. Subsequently, subjects with inadequate response to MTX who express signs of active disease at Screening are a commonly used subject population for clinical studies evaluating the efficacy of novel RA treatments in comparison with placebo. For JAK inhibitors, a 24-week treatment duration allows sufficient time for improvement in manifestations of active disease to be demonstrated and confirms that clinical benefit is sustained over time. Withholding subjects with sub-optimally treated disease from more effective treatments with a background MTX therapy for a maximum of 12 weeks is considered clinically and ethically acceptable.

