Consequently, each subject will remain in the study for a maximum of 29 weeks (from Screening visit to Follow-up visit).

A diagram of the study design can be found below.

| Week 1 - 12                | Week 13 – 24   |
|----------------------------|--|
| Randomized to placebo      | Responders (i.e., having at least 20% improvement on TJC68 and SJC66) remain on placebo |
|                            | Nonresponders re-randomized to 100 mg q.d.   |
|                            | Nonresponders re-randomized to 50 mg b.i.d.  |
| Randomized to 50 mg q.d.   | Responders remain on 50 mg q.d.   |
|                            | Nonresponders assigned to 100 mg q.d.   |
| Randomized to 25 mg b.i.d. | Responders remain on 25 mg b.i.d.   |
|                            | Nonresponders assigned to 50 mg b.i.d.  |
| Randomized to 100 mg q.d.  | Remain on 100 mg q.d.   |
| Randomized to 50 mg b.i.d. | Remain on 50 mg b.i.d.  |
| Randomized to 200 mg q.d.* | Remain on 200 mg q.d.*  |
| Randomized to 100 mg b.id* | Remain on 100 mg b.i.d.*  |

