## 8.1. ACR20, ACR50, ACR70 AND ACR-N

### 8.1.1. Parameters

ACR20 response when:

- $\geq 20\%$  improvement from baseline in SJC66, and
- $\geq 20\%$  improvement from baseline in TJC68, and
- $\geq 20\%$  improvement from baseline in at least 3 of the following 5 items:
  - Pain VAS (taken from the HAQ-DI)
  - Patient's Global Assessment of Disease Activity VAS
  - Physician's Global Assessment of Disease Activity VAS
  - Total HAQ-DI score
  - CRP.

Subjects who do not meet this criterion are non-responders.

If any of the 7 components of the ACR20 would be missing, then this missing component will be imputed using the value of the last preceding nonmissing visit. If all components are missing, then the derived ACR20 will remain missing. Imputation of such cases for the tables will be done there using LOCF or NRI like any other missing value.

Subjects who discontinue within the first week so that ACR20/50/70 responses cannot be determined will be classified as non-responders.

The ACR50 and ACR70 responses are derived using the same algorithm, but with 50% and 70% cutoffs respectively.

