**8.1.4. Tables after Week 12**

Tables will present only Weeks 12-16-20-24, unless specified otherwise. Tables will show the 15 arms of the “third efficacy analysis chapter”.

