**Table 14.2.1.1.24: ACR20 after Week 12: Frequency table**

Frequency table per time point, and per treatment group (15 arms).

The table will show:

- NRI in ITT
- LOCF in ITT
- observed-case in ITT (weeks 12 + 24)

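### The post-Week 12 ACR tables bound, but do not identify, how many Week 12 responders keep their response, which is the question the SAP sets for that analysis

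*SAP*

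**What the plan says.** SAP 2.1.1, Chapter 3 (from Week 12 on), divides subjects into seven arms of Week 12 responders who continue unchanged and eight arms of Week 12 non-responders. Of the first set it says: "This analysis will show whether Week 12 responders remain responders when treatment is continued unchanged".

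That section does not define the term. The notes to the study diagram in SAP 1.2 do: "Responder: at least 20% drop in TJC68 and SJC66 versus baseline". The design table in Protocol 8.1 gives the same joint-count rule, and this rule decides who switches in the placebo, 50 mg q.d. and 25 mg b.i.d. groups.

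ACR20, in SAP 8.1.1, needs the same two joint-count improvements plus 20% "improvement from baseline in at least 3 of the following 5 items". The section adds: "Subjects who do not meet this criterion are non-responders". The SAP therefore uses the responder label in two senses.

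For the ACR outputs after Week 12, SAP 8.1.4 says: "Tables will present only Weeks 12-16-20-24, unless specified otherwise". Table 14.2.1.1.24 is a frequency table of ACR20 by visit for each of the 15 arms. Tables 14.2.1.1.25 and .26 repeat it for ACR50 and ACR70.

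**The concern.** Whether responders remain responders is a conditional question: among subjects with the response at Week 12, what fraction still has it later? The ACR tables give a rate over the whole arm at each visit. If the arm is formed by joint counts, some of its members were not ACR20 responders at Week 12, and more were not ACR50 or ACR70 responders. The Week 24 rate then adds responses kept to responses newly gained, and losses can be offset by gains.

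No other planned ACR output fills the gap. The 24-week ACR tables are also per-visit rates, and time to response stops at Week 12 (SAP 8.1.1). The shift table planned for DAS28(CRP) belongs to a change-from-baseline table and is not a Week 12 to Week 24 transition.

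At stake is a descriptive statement about durability. Protocol 6.6 supports the 24-week duration partly because it "confirms that clinical benefit is sustained over time", and Chapter 3 is where the SAP says maintenance will be seen. Two arms with different loss of response could print identical rows.

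**Working it through.** **1. Arm count.** SAP 2.1.1 lists 7 continued responder arms and 8 non-responder arms: 7 + 8 = 15, the number in SAP 8.1.4.

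**2. Which rule forms the arms.** For placebo, 50 mg q.d. and 25 mg b.i.d. the structure settles it. Every listed non-responder in these groups is switched, and there is no arm for a subject who fails ACR20 but stays on treatment. For the four 100 and 200 mg/day groups nobody switches, and the joint-count rule is an inference from the general note in SAP 1.2.

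**3. Nesting.** ACR20 contains the joint-count condition, so every ACR20 responder is a joint-count responder but not the reverse. The non-responder arms are not affected in the same way: a subject who fails the joint-count rule cannot be an ACR20 responder on the same data, so later ACR20 in those arms is newly gained.

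**4. What the rates imply.** Let a and b be the ACR rates in an arm at Week 12 and Week 24. The proportion maintained lies between max(0, a + b − 1)/a and min(a, b)/a. Illustrative rates (assumed):

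| Week 12 | Week 24 | Lowest maintained | Highest maintained |
|---|---|---|---|
| 100% | 80% | 80% | 80% |
| 90% | 90% | 89% | 100% |
| 80% | 80% | 75% | 100% |
| 80% | 70% | 63% | 88% |
| 60% | 60% | 33% | 100% |

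In counts for the third row: 60 joint-count responders, 48 with ACR20 at each visit. At most 60 − 48 = 12 can be gained, so 36 to 48 of the 48 are kept, or 75% to 100%.

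**5. ACR50.** Assume 25 of 60 at both visits. Up to 60 − 25 = 35 could be gained, which exceeds 25, so the number kept is anywhere from 0 to 25. The logical range is 0% to 100%.

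**6. How far below 100% the Week 12 ACR20 rate might be.** Protocol 8.8.2 plans 85 subjects per arm and a placebo ACR20 rate of 20% to 40%. Assume joint-count response exceeds ACR20 by 0 to 20 percentage points. At 40% ACR20 (34 of 85), the continued-placebo arm holds 34 to 51 subjects, so its Week 12 ACR20 rate runs from 34/34 = 100% down to 34/51 = 67%. At 20% (17 of 85), it runs from 17/17 = 100% down to 17/34 = 50%.

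**7. Joint-count persistence.** Tables 14.2.1.5.7 to .9 describe joint counts after Week 12 in the same 15 arms. By cross-reference (SAP 8.5.4 to DAS28(CRP), then to SDAI/CDAI) they carry percent-change categories at Weeks 12 and 24 with a cut at −20%. If all members met the joint-count rule at Week 12, these later rates are already conditional on it, but for each count separately. With proportions t and s still meeting the threshold, both are met in max(0, t + s − 1) to min(t, s): 80% to 90% when each is 90%, and 60% to 80% when each is 80%. A change of exactly −20% also falls in the category of smaller improvement.

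**The case against.** A reader might infer that nothing planned bears on maintenance. The documents do not support that. The two visit rates bound ACR maintenance, tightly when the Week 12 rate is close to 100%, and the joint-count tables partly show persistence under the rule that forms the arms. If ACR20 were in fact the split in the 100 and 200 mg/day groups, their Week 24 ACR20 rate would be the exact maintenance figure, although ACR50 and ACR70 would remain unidentified. That mixture would also put columns with different definitions side by side.

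A second argument is that sustained benefit can be read as a group rate. The 24-week analysis gives Week 24 ACR20 by randomized group with non-responder imputation, and the 100 and 200 mg/day groups have no switching. That is a fair answer to the rationale in Protocol 6.6. It does not answer the narrower sentence in SAP 2.1.1, which concerns individual responders.

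Third, the numbers above are assumed, and the extremes need unlikely patterns: 0% for ACR50 requires all 25 responders to lose response while exactly 25 others gain it. This stands. The range shows what the tables leave open, not what to expect.

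Finally, Listing 16.2.6.1 gives ACR status per subject and visit, so persistence could be worked out later. That shows the fix is easy, but a listing is not a planned summary.

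**Conclusion.** The point holds as a gap between a stated aim and its output. The ACR tables after Week 12 bound maintenance of response but do not identify it. At an assumed 80% at both visits the uncertainty is 25 percentage points (75% to 100%), and at equal rates of 50% or less it is the full range. Joint-count persistence is only partly shown because the two counts are not combined.

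This rests on the joint-count rule applying in all seven continued arms, which is explicit for three and inferred for four, and on the SAP text alone, since the mock tables are in a separate document not available here.

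A reader might go further and infer that the gap misleads dose or regimen choice. The documents do not support this. SAP 4.5.3 makes the second-period comparison descriptive only, and Protocol 8.1 and SAP 6.2 tie preliminary dose selection to the Week 12 interim analysis. That analysis and the primary Week 12 endpoint are untouched. This is a cheap improvement to a descriptive analysis.

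**What to change.** 1. State in SAP 2.1.1 that the Week 12 responder split uses the joint-count rule in all seven original groups.
2. In Tables 14.2.1.1.24, .25 and .26, add for each continued arm the number and percentage of Week 12 ACR20 (respectively ACR50, ACR70) responders who still have that response at Weeks 16, 20 and 24, using non-responder imputation. Add the number of Week 12 non-responders on that criterion who gain it.
3. Base the statement on maintained response on those rows, and label the existing rows as ACR rates in joint-count responders.
4. Note that the new rows are descriptive. They condition on an outcome after randomization, so they are not a randomized comparison between doses.

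The cost is a small programming addition from ACR status already derived and listed. The downside is smaller denominators, hence less precise percentages, and slightly longer tables.
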